7.6.17 Lip Texture Evaluation

Lip texture will be assessed by the Investigator as normal or abnormal prior to treatment at Visit 1/Day 1 and at Visit 2/Month 1 and Visit 3/Month 2 (Table 1).

Table 1. Lip Texture Scoring Criteria

Normal	Abnormal		
	Mild	Moderate	Severe
Texture of the lip is even without visible undulations or excessive coarseness beyond that expected for stated age	The lip shows a single area of textural irregularity (a small papule, area of excess smoothness, focal absence of perpendicular lines) can be visualized only with close inspection	The lip shows more than one area of textural irregularity (a small papule, area of excess smoothness, focal absence of perpendicular lines) can be visualized only with close inspection. Or The lip shows one area of textural irregularity (less than ¼ of the lip area) at a conversational distance.	The lip shows two or more areas of textural irregularity (a small papule, area of excess smoothness, focal absence of perpendicular lines) can be visualized at a conversational distance. Or The lip shows one area of textural irregularity (more than ¼ of the lip area) at conversational distance

7.6.18 Lip Firmness Evaluation

Lip firmness will be assessed by the Investigator as normal or abnormal prior to treatment at Visit 1/Day 1 and at Visit 2/Month 1 and Visit 3/Month 2 (Table 2).

Table 2. Lip Firmness Scoring Criteria

Normal	Abnormal		
	Mild	Moderate	Severe
Lip is supple when compressed laterally and surface distorted readily with minimal pressure. Pressure with a narrow diameter instrument (cotton-tipped applicator, toothpick, etc) causes a focal depression in the surface of the lip. Upon palpation, lip is absent of abnormal structures such as scars or lumps; normal product feel without being visible.	Lip is slightly firm with lateral compression or required slightly greater than normal pressure to distort the surface. Upon palpation, an abnormal structure such as a scar or lump is felt, but is not visible.	Lip is firm with lateral compression or requires distinctly greater than normal pressure to distort the surface or pressure with a narrow diameter instrument (cotton-tipped applicator or toothpick) causes a broader depression in the surface of the lip. Upon palpation, an abnormal structure such as a scar or lump is felt and is visible.	Lip is very firm with lateral compression or requires significantly greater than normal pressure to distort the surface. Upon palpation, an abnormal structure such as a scar or lump is felt and is visually distracting.

7.6.19 Lip Symmetry Evaluation

Lip symmetry will be assessed by the Investigator as normal or abnormal prior to treatment at Visit 1/Day 1 and at Visit 2/Month 1 and Visit 3/Month 2 (Table 3).

Table 3. Lip Symmetry Scoring Criteria

Normal	Abnormal		
	Mild	Moderate	Severe
One side of the lip balanced or mirrored the other side	One side of the lip shows a 1 mm or less difference in height or a 1 mm or less difference in the length of the vermilion at repose.	One side of the lip shows a 1.1 mm to 2 mm difference in height or a 1.1 to 2 mm difference in the length of the vermilion at repose	One side of the lip shows a greater than 2 mm difference in the height or a greater than 2 mm difference in the length of the vermilion at repose.

7.6.20 Lip Movement/Function Evaluation

Lip movement/function will be evaluated by the Investigator as normal or abnormal prior to treatment at Visit 1/Day 1 and at Visit 2/Month 1 and Visit 3/Month 2 as the subject’s ability to pucker lips, blowing and pronunciation of words that begin with the letter “W” such as water, work, week and wind.

7.6.21 Subject Satisfaction with Lips (Visual Analog Scale [VAS])

Subjects will be asked to assess their overall satisfaction with their lips at using a 100 mm VAS scale from 0 = Very Unsatisfied to 100 = Very Satisfied at Visit 2/Month 1 and Visit 3/Month 2 (Figure 1).

Figure 1 Visual Analog Scale for Subject Satisfaction

7.6.22 Subject Diary Card

A diary card will be dispensed to each enrolled subject at Visit 1/Day 1. The subject will be instructed to complete the diary card to record any AEs experienced during the 2 weeks after receiving treatment. The diary card will be collected at Visit 2/Month 1.

7.6.23 Adverse Events and Serious Adverse Events Assessment

See Section 7.9 for instructions on the assessment and reporting of AEs and SAEs and Section 7.9.7 for instructions on reporting SAEs to the Sponsor or designee.

7.7 Visit-Specific Procedures

The following sections outline the procedures required at each visit.

7.7.1 Visit 1/Day 1: Treatment

This is the same as Visit 5 of Protocol PRO 2018-02 and assessments performed for that study (e.g., LFGS and POL assessments) do not need to be repeated for this study.

- Obtain written informed consent
- Evaluate inclusion/exclusion criteria
- Update the medical history and demographic information as needed from that at entry to Protocol 2018-02
- Perform vital signs (temperature, heart rate, blood pressure, and respiratory rate)
- Vision evaluation (Snellen visual acuity, confrontational visual fields, ocular motility)
- Obtain/record concomitant medications/treatments
- Perform urine pregnancy test for all women of childbearing potential
- LFGS assessment
- POL assessment
- Lip function evaluation prior to treatment administration
- Lip sensation evaluation prior to treatment administration

- Lip texture evaluation prior to treatment administration
- Lip firmness evaluation prior to treatment administration
- Lip symmetry evaluation prior to treatment administration
- Lip movement/function prior to treatment administration
- Treatment administration
- Vision evaluation (Snellen visual acuity, confrontational visual fields, ocular motility)
- Investigator Ease of Use assessment
- Assess AEs
- Dispense subject diary card
- Schedule next visit
- Complete CRFs

7.7.2 Telephone Contacts on Day 3 and Day 14

- Assess AEs
- Assess concomitant medications/treatments
- Confirm adherence to prohibited treatments/medications

7.7.3 Visit 2/Day 28 (± 2 days): Month 1

- LFGS assessment
- POL assessment
- pGAI assessment
- iGAI assessment
- Lip function evaluation
- Lip sensation evaluation
- Lip texture evaluation
- Lip firmness evaluation
- Lip symmetry evaluation
- Lip movement/function
- Vision evaluation (Snellen visual acuity, confrontational visual fields, ocular motility)
- Assess AEs
- Swelling assessment
- Assess concomitant medications/treatments
- Subject satisfaction with lips (VAS)

- Complete CRFs

7.7.4 Visit 3/Day 56 (\pm 4 days): Month 2 End of Study Visit/Early Termination

- LFGS assessment
- POL assessment
- pGAI assessment
- iGAI assessment
- Lip function evaluation
- Lip sensation evaluation
- Lip texture evaluation
- Lip firmness evaluation
- Lip symmetry evaluation
- Lip movement/function
- Vision evaluation (Snellen visual acuity, confrontational visual fields, ocular motility)
- Assess AEs
- Swelling assessment
- Assess concomitant medications/treatments
- Subject satisfaction with lips (VAS)
- Complete CRFs

7.7.5 Telephone Contact on Day 168 (Month 6) \pm 7 days

- Assess AEs
- Assess concomitant medications/treatments
- Confirm adherence to prohibited treatments/medications

7.7.6 Unscheduled Visit

An unscheduled visit is allowed at any time if in the investigator's opinion it is warranted. The following procedures may be performed at the Unscheduled Visit if required.

- LFGS assessment
- POL assessment
- pGAI assessment
- iGAI assessment
- Lip function evaluation
- Lip sensation evaluation

- Lip texture evaluation
- Lip firmness evaluation
- Lip symmetry evaluation
- Lip movement/function
- Vision evaluation (Snellen visual acuity, confrontational visual fields, ocular motility)
- Assess AEs
- Swelling assessment
- Subject satisfaction with lips (VAS)
- Assess concomitant medications/treatments
- Complete CRFs

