3.1 Study Design

For the purpose of exploring the above objectives, the study will be conducted as a multicenter, open-label clinical study of retreatment with PN40082 of subjects seeking lip augmentation who initially received treatment with either PN40082 or Restylane Silk in the prior PRO 2018-02 study. Subjects meeting the inclusion/exclusion criteria will receive a single additional treatment with PN40082.

Visits will occur at:

- Visit 1 / Day 1 – baseline and treatment. This is the same visit as Visit 5 (Day 168) of Protocol PRO 2018-02.
- Visit 2 / Day 28 (± 2 days) / Month 1 – interim visit
- Visit 3 / Day 56 (± 4 days) / Month 2 – End of Study (EOS) Visit.

Telephone contacts for safety follow-up will occur at:

- Day 3 (± 2 days) - Safety follow-up telephone call
- Day 14 (± 2 days) – Safety follow-up telephone call
- Day 168 (± 7 days) / Month 6 – Safety follow-up telephone call

Evaluations include:

- Lip Fullness Grading Scale (LFGS) (Overall lip fullness considering both lips together, fullness of the upper lip and fullness of the lower lip)
- Perioral lines at rest severity scale (POL) (Overall perioral lines at rest severity considering both lips together, perioral lines at rest severity of the upper lip and perioral lines at rest severity of the lower lip)
- Patient Global Aesthetic Improvement (pGAI)
- Investigator Global Aesthetic Improvement (iGAI)
- Swelling Assessment
- Subject Satisfaction with Lips Assessment (using VAS)

Safety will be assessed by monitoring adverse events (AEs) and concomitant medications at all study visits. Other Safety evaluations include lip function, lip sensation, lip texture, lip firmness, lip symmetry and lip movement/function. Other evaluations include Investigator Ease of Use Assessment.

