5.6.3 Other Variables

Investigator Ease of Use Assessment

Overall ease of use of the device will be evaluated by the Treating Investigator using the numerical rating scale (NRS) from 0 being not easy to 10 being most easy at Visit 1/Day. It will be summarized for all retreated subjects descriptively with mean, SD, minimum, median, and maximum.

Lip Evaluations

Lip function, lip sensation, lip texture, lip firmness, lip symmetry, and lip movement/function will be evaluated by the Blinded Evaluating Investigator at each visit. These variables will be summarized using frequency and percent of subjects by categories of incidence.

Concomitant Medications

Concomitant medications will be coded using the World Health Organization (WHO) Drug Dictionary, Version March 2013 or later, and will be presented in data listings.

6 Tables and Listings

The following is an example of tables and listings that will be included in the clinical study report. Tables and listings may be modified as needed during the data analyses.

7 Appendices

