LFGS: 0=Very Thin Lips, 1=Thin Lips, 2=Moderately Thick Lips, 3=Thick Lips, 4=Full Lips.

Source: Listing 16.2.6.1

O:\Studies\Prolenium\SYM 2018-03\Biometrics\Programs\Tables\xxx.sas ran on Month Day, Year at hh:mm on data from Month, Day, Year.

Note:

Table 14.2.1 will be used as the shell for the following table:

Table 14.2.2 – Efficacy: Change from Baseline in Overall Perioral Lines at Rest (POL) Severity Scale at Visit 2/Month 1 and Visit 3/Month 2

With first footnote changed to the following:

POL severity: 0=None, 1=Mild, 2=Moderate, 3=Severe.

Table 14.2.3 – Efficacy: Patient Global Aesthetic Improvement (pGAI) by Visit

Study Visit	Category	PRO 2018-02 PN40082	PRO 2018-02 Restylane Silk	Total
Visit 1/Day 1 Retreatment	N	0	0	0
	1 = Worse	0 (0%)	0 (0%)	0 (0%)
	2 = No Change	0 (0%)	0 (0%)	0 (0%)
	3 = Improved	0 (0%)	0 (0%)	0 (0%)
	4 = Much Improved	0 (0%)	0 (0%)	0 (0%)
	5 = Very Much Improved	0 (0%)	0 (0%)	0 (0%)
Visit 2/Month 1	...			
Visit 3/Month 2	...			

Source: Listing 16.2.6.2
O:\Studies\Prolenium\SYM 2018-03\Biometrics\Programs\Tables\xxx.sas ran on Month Day, Year at hh:mm on data from Month, Day, Year.

Note:

Table 14.2.3 will be used as the shell for the following table:

Table 14.2.4 – Efficacy: Investigator Global Aesthetic Improvement (iGAI) by Visit

Table 14.2.5 – Efficacy: Swelling Assessment by Visit

Study Visit	Category	PRO 2018-02 PN40082	PRO 2018-02 Restylane Silk	Total
Visit 1/Day 1 Retreatment	N	0	0	0
	0 = None	0 (0%)	0 (0%)	0 (0%)
	1 = Minimal	0 (0%)	0 (0%)	0 (0%)
	2 = Mild	0 (0%)	0 (0%)	0 (0%)
	3 = Moderate	0 (0%)	0 (0%)	0 (0%)
	4 = Severe	0 (0%)	0 (0%)	0 (0%)
Visit 2/Month 1	...			
Visit 3/Month 2	...			

Source: Listing 16.2.6.2

O:\Studies\Prolenium\SYM 2018-03\Biometrics\Programs\Tables\xxx.sas ran on Month Day, Year at hh:mm on data from Month, Day, Year.

Table 14.2.6 – Efficacy: Subject Satisfaction with Lips VAS by Visit

Study Visit	Statistics	PRO 2018-02 PN40082	PRO 2018-02 Restylane Silk	Total
Visit 1/Day 1 Retreatment	N	0	0	0
	Mean ± SD	0.0 ± 0.00	0.0 ± 0.00	0.0 ± 0.00
	Median	0.0	0.0	0.0
	Min, Max	0, 0	0, 0	0, 0
Visit 2/Month 1	...			
Visit 3/Month 2	...			

Source: Listing 16.2.6.2

O:\Studies\Prolenium\SYM 2018-03\Biometrics\Programs\Tables\xxx.sas ran on Month Day, Year at hh:mm on data from Month, Day, Year.

Table 14.3.1.1 – Exposure to Study Product and Investigator Ease of Use Assessment (Upper Lips) at Visit 1/Day 1 Retreatment

	Statistics	PRO 2018-02 PN40082	PRO 2018-02 Restylane Silk	Total

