Table 14.3.3.3 – Treatment-Emergent Adverse Events (TEAEs) Excluding Vascular Injections/Visual Events by MedDRA System Organ Class, Preferred Term, and Causality

Table 14.3.3.4 – Treatment-Emergent Adverse Events (TEAEs) Excluding Vascular Injections/Visual Events by MedDRA System Organ Class, Preferred Term, and Number of Injections

With footnote regarding data source change to “Source: Listing 16.2.7.1.2”.

Table 14.3.4.1 – Lip Function and Lip Sensation Tests by Visit

Study Visit	Category	PRO 2018-02 PN40082	PRO 2018-02 Restylane Silk	Total
Was the subject able to sip liquid through a straw?				
Visit 1/Day 1 (Prior to injection)	N	0	0	0
	n (%) Yes	0 (0%)	0 (0%)	0 (0%)
Visit 2/Month 1	N	0	0	0
	n (%) Yes	0 (0%)	0 (0%)	0 (0%)
Visit 3/Month 2	N	0	0	0
	n (%) Yes	0 (0%)	0 (0%)	0 (0%)
Was the subject able to feel sensation of a 0.4G monofilament at three points on the upper lip and three points on the lower lip?				
Visit 1/Day 1 (Prior to injection)				
...				
Was the subject able to feel sensation of a cotton wisp at three points on the upper lip and three points on the lower lip?				
Visit 1/Day 1 (Prior to injection)				
...				

Source: Listing 16.2.4.8

O:\Studies\Prollenium\SYM 2018-03\Biometrics\Programs\Tables\xxx.sas ran on Month Day, Year at hh:mm on data from Month, Day, Year.

Table 14.3.4.2 – Lip Texture Evaluation by Visit

Study Visit	Category	PRO 2018-02 PN40082	PRO 2018-02 Restylane Silk	Total
Visit 1/Day 1 (Prior to injection)	N	0	0	0
	n (%) Normal	0 (0%)	0 (0%)	0 (0%)
	n (%) Abnormal	0 (0%)	0 (0%)	0 (0%)
	- n (%) Abnormal: Mild	0 (0%)	0 (0%)	0 (0%)
	- n (%) Abnormal: Moderate	0 (0%)	0 (0%)	0 (0%)
	- n (%) Abnormal: Severe	0 (0%)	0 (0%)	0 (0%)
Visit 2/Month 1	...			
	...			
Visit 3/Month 2				

Source: Listing 16.2.4.9

O:\Studies\Prolenium\SYM 2018-03\Biometrics\Programs\Tables\xxx.sas ran on Month Day, Year at hh:mm on data from Month, Day, Year.

Note:

Table 14.3.4.2 will be used as the shell for the following table:

Table 14.3.4.3 – Lip Firmness Evaluation by Visit

Table 14.3.4.4 – Lip Symmetry Evaluation by Visit

Table 14.3.4.5 – Lip Movement/Function Evaluation by Visit

Study Visit	Category	PRO 2018-02 PN40082	PRO 2018-02 Restylane Silk	Total
Visit 1/Day 1 (Prior to injection)	N	0	0	0
	n (%) Normal – Subject’s ability to pucker lips	0 (0%)	0 (0%)	0 (0%)
	n (%) Normal – Subject’s ability to blow with lips	0 (0%)	0 (0%)	0 (0%)
	n (%) Normal – Subject’s ability to pronounce words that begin with “W”	0 (0%)	0 (0%)	0 (0%)

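### Graded lip and swelling results from unscheduled visits enter no lip or swelling summary table, although no clinic examination is scheduled on Days 2-25 or after Visit 3

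*Protocol*

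**What the plan says.** **Unscheduled visits.** Protocol 7.7.6 states: "An unscheduled visit is allowed at any time", provided that the investigator considers it warranted. It adds: "The following procedures may be performed at the Unscheduled Visit if required". The list that follows contains the six lip evaluations, the Swelling Assessment, the vision tests and adverse event (AE) assessment. The schedules in Protocol section 2 and SAP 7.2 mark the lip, swelling and vision items in the unscheduled column as done if or as needed.

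**Scheduled contacts.** After treatment on Day 1, the first clinic visit is "Visit 2 / Day 28 (± 2 days) / Month 1 – interim visit" (SAP 3.1). Before it there are only telephone calls, on Day 3 and then "Day 14 (± 2 days) – Safety follow-up telephone call". Visit 3 is on Day 56 (± 4 days). After that only the Day 168 call remains, and a subject completes the study at that call (Protocol 7.2).

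**Analysis.** SAP 5.6 names the lip evaluations among the key safety variables. SAP 5.6.3 says of them: "These variables will be summarized using frequency and percent of subjects by categories of incidence". The shells, for example "Lip Texture Evaluation by Visit" (Table 14.3.4.2) and "Efficacy: Swelling Assessment by Visit" (Table 14.2.5), have rows for Visits 1, 2 and 3 only. The SAP has no rule for unscheduled results and no row for the worst result after injection. SAP 5.1 puts all data points of the retreatment period in listings, and Listing 16.2.1.2 counts unscheduled visits.

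**The concern.** The plan provides for graded examinations at visits called because the investigator sees a reason, and then gives those grades no place in the tables built on the same scales. The tables describe status near Day 28 and Day 56. A graded abnormality that is examined at, say, Day 10 and gone by Visit 2, or that first appears at Day 90, does not change them.

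The product's own Instructions for Use (Protocol Appendix 2) warn both of inflammatory symptoms beginning soon after lip treatment and of inflammatory papules of delayed onset. The texture scale grades papules and the firmness scale grades lumps (Protocol 7.6.17 and 7.6.18). Both risk periods lie partly outside the tabulated visits. At stake is the completeness of a graded safety summary. No test, error rate or sample size is involved.

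**Working it through.** The plan states no rate or sample size on this point, so there is no figure to reproduce. The check has three parts.

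**1. Days without a scheduled clinic examination** (day ± window, with Day 1 the treatment day; Protocol section 2, SAP 3.1)

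| Contact | Window | Type |
|---|---|---|
| Day 3 | 1 to 5 | telephone |
| Day 14 | 12 to 16 | telephone |
| Visit 2 | 28 − 2 = 26 to 28 + 2 = 30 | clinic |
| Visit 3 | 56 − 4 = 52 to 56 + 4 = 60 | clinic |
| Day 168 | 161 to 175 | telephone |

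- Treatment to the earliest Visit 2: Days 2-25, that is 25 − 2 + 1 = 24 days. With Visit 2 at its latest, Days 2-29, that is 28 days.
- Between the latest Visit 2 and the earliest Visit 3: Days 31-51, that is 51 − 31 + 1 = 21 days.
- After the latest Visit 3 up to the final call: Days 61-168, that is 168 − 61 + 1 = 108 days.

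In these intervals an unscheduled visit is the only route to a lip or swelling grade.

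**2. Where a grade from an unscheduled visit goes**

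| Result | Lip or swelling table | TEAE tables | Listing |
|---|---|---|---|
| Abnormal grade, also recorded as an AE | no row | yes, on the AE severity scale | yes |
| Abnormal grade, not recorded as an AE | no row | no | yes |
| Vision examination | no vision table for any visit | only if recorded as a visual AE | yes (16.2.4.7) |

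The second line is the gap. Four provisions show why the AE route need not close it:

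- No text available to me makes an abnormal lip or swelling grade an AE automatically. Part of Protocol 7.9.7 is not in that text.
- Specific AEs are not to be elicited (Protocol 7.9.5), and subjects are not to be asked specifically about swelling (7.6.14).
- Diary events that outlast the diary are recorded as AEs at the investigator's discretion (7.9.8).
- AE severity is graded by tolerability and effect on daily activity (7.9.6.1), whereas texture, firmness and symmetry are graded by visible, palpable or measured findings (7.6.17 to 7.6.19). One grade cannot be converted into the other.

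**3. Possible size (illustration only)**

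The documents give no durations. Assume onset on Day 2 and exponential duration with median m days. The share still present on Day d is 0.5^((d − 2)/m).

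| m (assumed) | Day 26 | Day 28 | Day 30 |
|---|---|---|---|
| 3 | 0.4% | 0.2% | 0.2% |
| 7 | 9.3% | 7.6% | 6.2% |
| 14 | 30.5% | 27.6% | 25.0% |
| 30 | 57.4% | 54.8% | 52.4% |

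Short-lived early findings would thus mostly be gone by Visit 2. How many are ever graded depends on how many unscheduled examinations take place, which is unknown. If k of an assumed 120 examined subjects had an abnormal grade only at an unscheduled visit, the proposed row would exceed one built from scheduled visits alone by k/120: 0 for k = 0, 3.3 percentage points for k = 4, 5.0 for k = 6 and 8.3 for k = 10. The protocol expects fewer than 158 subjects, so each such subject counts for more than 1/158 = 0.6 points.

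**The case against.** The strongest reply is that early reactions are the business of the AE system, which is well supplied here. There is a two-week diary, there are calls on Days 3 and 14, and AEs are assessed at unscheduled visits. All AEs are recorded (Protocol 7.9.1), and swelling and bruising at the injection site are named as expected events (7.9.3.1). The TEAE tables separate reports by subject and by investigator and give severity. For the vascular/visual group they also give duration. The mock record in Listing 16.2.7.1.1 is an injection-site swelling lasting from Day 2 to Day 5. All of this stands. A reader might infer that problems found at unscheduled visits reach no summary at all; the documents do not support that.

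A reader might also extend the point to vision. That fails: vision examinations are tabulated for no visit, so there is no vision abnormality rate to distort. Vision changes are AEs of special interest (Protocol 7.9.3.4), and visual TEAEs are summarized separately.

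Thirdly, tables by visit are correct for what they show, namely status at Months 1 and 2. It would be wrong to call them biased against a true cumulative rate. Self-selected examinations could not supply such a rate in any case. This also stands, and it limits what an added row may be called.

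Finally, the SAP calls its shells examples that may be modified (SAP 6), and no text excludes unscheduled data. That weakens any charge of deliberate omission. It also leaves the decision until open-label results are visible, so a rule written beforehand is preferable. The Swelling Assessment is an efficacy variable in SAP 5.5, so for swelling the point is completeness of a graded result rather than of a designated safety endpoint.

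**Conclusion.** The gap is real but narrow. As the shells stand, a lip or swelling grade obtained at an unscheduled visit enters no table on its own scale. If it is not also recorded as an AE, it appears only in a listing. The intervals concerned are at least Days 2-25 and the whole period after Visit 3.

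The conclusion rests on two assumptions: that the shells will be used as drawn, and that no instruction outside the available text makes every abnormal grade an AE. The effect on reported abnormality could be nil if few unscheduled examinations occur, and the percentages above are illustrations. The Month 1 and Month 2 rows remain valid, and no inference depends on them. The addition is worth making because it is cheap and uses data that the protocol already provides for.

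**What to change.** In SAP 5.5.1 and 5.6.3, state how unscheduled results are handled, and change the shells as follows:

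- Keep the by-visit rows.
- Add to Tables 14.3.4.1 to 14.3.4.5 and to Table 14.2.5 a row *Worst result at any scheduled or unscheduled visit after injection*, by prior arm and overall. Count each subject once. For the yes/no tests, the worst result is any failure or abnormal finding.
- Use as denominator the retreated subjects examined on that scale at least once after injection.
- Report the number of subjects with at least one unscheduled examination on that scale, by prior arm and overall.
- Add a footnote that unscheduled examinations are optional and self-selected, so the row gives the observed worst grade and not a full incidence rate.

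No vision table is needed for this purpose. The cost is minor shell and programming work, with no new data collection. Reported abnormality rates may become slightly less favourable.
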